#### 7.2 Adverse Event Characteristics

- **CTCAE term (AE description) and grade:** The descriptions and grading scales found in the revised NCI Common Terminology Criteria for Adverse Events (CTCAE) version 5.0 will be utilized for AE reporting. All appropriate treatment areas should have access to a copy of the CTCAE version 5.0. A copy of the CTCAE version 5.0 can be downloaded from the CTEP web site  
[http://ctep.cancer.gov/protocolDevelopment/electronic\\_applications/ctc.htm](http://ctep.cancer.gov/protocolDevelopment/electronic_applications/ctc.htm).
- **For expedited reporting purposes only:**
  - AEs for the agent(s) that are listed above should be reported only if the adverse event

varies in nature, intensity or frequency from the expected toxicity information which is provided.

- **Attribution** of the AE:
  - Definite – The AE *is clearly related* to the study treatment.
  - Probable – The AE *is likely related* to the study treatment.
  - Possible – The AE *may be related* to the study treatment.
  - Unlikely – The AE *is doubtfully related* to the study treatment.
  - Unrelated – The AE *is clearly NOT related* to the study treatment.

### 7.3        Serious Adverse Events

A serious adverse event (SAE) is any adverse event that occurs after the initial dose of study treatment, during treatment, or within 30 days of the last dose of treatment that results in one of the following outcomes:

- Death
- Hospitalization for greater than 24 hours
- Prolonging an existing inpatient hospitalization
- A life-threatening experience (that is, immediate risk of dying)
- Persistent or significant disability/incapacity
- Congenital anomaly/birth defect
- Considered significant by the investigator for any other reason

Previously planned (prior to signing the informed consent form) surgeries, and non-disease related elective surgeries planned during the course of the study, should not be reported as SAEs unless the underlying medical condition has worsened or appeared during the course of the study. Events that occur prior to the first administration of study medication should not be reported as SAEs.

Preplanned hospitalizations or procedures for pre-existing conditions that are already recorded in the patient's medical history at the time of study enrollment should not be considered SAEs. Hospitalization or prolongation of hospitalization without a precipitating clinical AE (e.g., for the administration of study therapy or other protocol-required procedure) should not be considered SAEs.

Important medical events that may not result in death, be life-threatening, or require hospitalization may be considered SAEs when, based on appropriate medical judgment, they may jeopardize the patient and may require medical or surgical intervention to prevent one of the outcomes listed in this definition.

Death due to disease progression should not be reported as an SAE unless the investigator deems it to be related to the use of study drug.

Study site personnel must alert Eli Lilly of any SAE as soon as possible and no later than 1

business day of the investigator receiving notification of the SAE experienced by a patient participating in the study. The SAE reports should be on a standard reporting form (e.g. CIOMS, local institutional SAE form, MedWatch 3500a, or similar) and are to be sent to Eli Lilly via email: [[name]\\[contact]](mailto:[contact]).

#### 7.4 Adverse Event Reporting

- 7.4.1 In the event of an unanticipated problem or life-threatening complications treating investigators must immediately notify the Overall PI.
- 7.4.2 Investigators **must** report to the Overall PI any adverse event (AE) that occurs after the initial dose of study treatment, during treatment, or within 30 days of the last dose of treatment on the local institutional SAE form.
- 7.4.3 For Multi-Center Trials where a DF/HCC investigator is serving as the Sponsor, each participating institution **must** abide by the reporting requirements set by the DF/HCC. This applies to any medical event equivalent to an unexpected grade 2 or 3 with a possible, probable or definite attribution, unexpected grade 4 toxicities, and grade 5 (death) regardless of study phase or attribution.

##### 7.4.4 DF/HCC Adverse Event Reporting Guidelines

Investigative sites within DF/HCC will report AEs directly to the DFCI Office for Human Research Studies (OHRS) per the DFCI IRB reporting policy.

Other investigative sites will report AEs to their respective IRB according to the local IRB's policies and procedures in reporting adverse events. A copy of the submitted institutional AE form should be forwarded to the Overall PI within the timeframes detailed in the table below.

| Attribution   | DF/HCC Reportable Adverse Events(AEs)  |                         |                     |                                 |
|---|--|-------------------------|---------------------|---------------------------------|
|   | Gr. 2, 3, & 4 AE Expected # | Gr. 2 & 3 AE Unexpected | Gr. 4 AE Unexpected | Gr. 5 AE Expected or Unexpected |
| Unrelated
Unlikely   | Not required                           | Not required            | 5 calendar days     | 24 hours*                       |
| Possible
Probable
Definite  | Not required                           | 5 calendar days         | 5 calendar days     | 24 hours*                       |
| # Please note, an event that presents at a higher severity than what is currently listed within the protocol and/or current consent as expected would be considered unexpected and reportable.                            |  |                         |                     |                                 |
| * For participants enrolled and actively participating in the study or for AEs occurring within 30 days of the last intervention, the AE should be reported within 1 business day of learning of the event. |  |                         |                     |                                 |

The Overall PI will submit AE reports from outside institutions to the DFCI OHRS according to DFCI IRB policies and procedures in reporting adverse events.

### **7.5 Reporting to the Food and Drug Administration (FDA)**

The Overall PI, as study sponsor, will be responsible for all communications with the FDA. The Overall PI will report to the FDA, regardless of the site of occurrence, any serious adverse event that meets the FDA's criteria for expedited reporting following the reporting requirements and timelines set by the FDA.

### **7.6 Reporting to Hospital Risk Management**

Participating investigators will report to their local Risk Management office any participant safety reports, sentinel events or unanticipated problems that require reporting per institutional policy.

### **7.7 Routine Adverse Event Reporting**

All Adverse Events **must** be reported in routine study data submissions to the Overall PI on the toxicity case report forms. **AEs reported through expedited processes (e.g., reported to the IRB, FDA, etc.) must also be reported in routine study data submissions.**

[figure not shown]
## **8. PHARMACEUTICAL INFORMATION**

A list of the adverse events and potential risks associated with the investigational administered in this study can be found in **Section 7.1**.

### **8.1 LY3214996**

**Chemical Name:** 4H-Thieno[2,3-c]pyrrol-4-one, 5,6-dihydro-6,6-dimethyl-2-[2-[(1-methyl-1H-pyrazol-5-yl)amino]-4-pyrimidinyl]-5-[2-(4-morpholinyl)ethyl]-

**Chemical Structure:**

**Structure of LY3214996.**

**Molecular Weight:** 453.57

**Molecular Formula:** C22H27N7O2S

**Description:** White to light brown powder

**Solubility:** Water: 0.06 mg/mL; Methanol: 7.8 mg/mL

#### 8.1.1 **Form**

The drug product is supplied as capsules. Each capsule contains LY3214996 equivalent to 25 mg or 100 mg of the base compound, with no inactive ingredients.

#### 8.1.2 **Storage and Stability**

The drug product should be stored at room temperature (10°C to 30°C).

#### 8.1.3 **Handling**

Qualified personnel, familiar with procedures that minimize undue exposure to themselves and the environment, should undertake the preparation, handling, and safe disposal of the chemotherapeutic agent in a self-contained and protective environment.

#### 8.1.4 **Availability**

LY3214996 is an investigational agent that will be supplied by Eli Lilly and Company.

#### 8.1.5 **Administration**

LY3214996 administration instructions:

- LY3214996 will be administered by mouth once daily continuously throughout each treatment cycle.
- Participants should be advised to take their dose at approximately the same time each day, a ± 4 hour dosing window is allowed. Doses that would occur outside of this time frame should be considered missed and should not be administered.
- Participants should be advised to fast for at least 1 hour prior to each dose, and to continue fasting for at least 1 hour after each dose. Water is permitted during the fasting period.
- If a participant vomits following a dose, the dose should not be re-taken. The participant should be advised to continue with their next regularly scheduled dose as clinically appropriate.
- LY3214996 should be swallowed whole, capsules should not be opened, chewed, or crushed.
- Refer to **Section 5.4** for anti-emetic regimen information.

#### 8.1.6 **Ordering**

LY3214996 will be ordered by site pharmacy personnel from Eli Lilly and Company.

#### 8.1.7 Accountability

The investigator, or a responsible party designated by the investigator, should maintain a careful record of the inventory and disposition of the agent using the NCI Drug Accountability Record Form (DARF) or another comparable drug accountability form. (See the NCI Investigator's Handbook for Procedures for Drug Accountability and Storage.)

[figure not shown]
#### 8.1.8 Destruction and Return

Expired, returned, or unused supplies of LY3214996 should be destroyed according to local institutional policies. Destruction will be documented in the Drug Accountability Record Form.

### 8.2 Hydroxychloroquine Sulfate (HCQ, Plaquenil®)

**Chemical Name:** 2-[[4-[(7-Chloro-4-quinolyl) amino]pentyl] ethylamino]ethanol sulfate (1:1)

**Chemical Structure:**

**Molecular Weight:** 433.95

**Molecular Formula:** C18H26ClN3O2·H2SO4

**Description:** White or practically white, crystalline powder

**Solubility:** Freely soluble in water, practically insoluble in alcohol, chloroform, and in ether

#### 8.2.1 Form

Please refer to the FDA package insert. HCQ tablets contain 200 mg hydroxychloroquine sulfate, equivalent to 155 mg base, and are for oral administration. Inactive Ingredients: Dibasic calcium phosphate USP, hypromellose USP, magnesium stearate NF, polyethylene glycol 400 NF, polysorbate 80 NF, corn starch, titanium dioxide USP, carnauba wax NF, shellac NF, black iron oxide NF.

#### 8.2.2 Storage and Stability

Please refer to the FDA package insert.

#### 8.2.3 Handling

Qualified personnel, familiar with procedures that minimize undue exposure to themselves and the environment, should undertake the preparation, handling, and safe disposal of the agent in a self-contained and protective environment in accordance with local institutional standards of practice.

#### 8.2.4 Availability

HCQ is an FDA approved drug that is commercially available.

#### 8.2.5 Administration

Only participants enrolled to the **Safety Lead-in Cohort, Arm 1**, or who cross-over on **Arm 2** will receive treatment with HCQ. Instructions for administration of HCQ:

- HCQ will be administered by mouth twice daily continuously throughout each treatment cycle.
- Participants should be advised to take their doses approximately 12 hours apart, a  $\pm$  4 hour dosing window is allowed. Doses that would occur outside of this time frame should be considered missed and should not be administered.
- Participants should be advised to take each dose with a meal (or within 30 minutes of eating) or with a glass of milk.
- If a participant vomits following a dose, the dose should not be re-taken. The participant should be advised to continue with their next regularly scheduled dose as clinically appropriate.
- HCQ should be swallowed whole, tablets should not be dissolved, chewed, or crushed.

#### 8.2.6 Ordering

HCQ is an FDA approved commercially available agent that should be ordered by site pharmacy personnel per local institutional standards of practice. The cost of HCQ will be covered by the research trial, it will not be billed to patient insurance.

#### 8.2.7 Accountability

HCQ accountability will be handled in accordance with local institutional standards of practice.

#### 8.2.8 Destruction and Return

Expired, returned, or unused supplies of HCQ should be destroyed according to local institutional policies.

### 9. BIOMARKER, CORRELATIVE, AND SPECIAL STUDIES

### **9.1        Tumor Biopsy Collection**

Core needle, incisional, or excisional biopsies may be obtained for analysis at the time points indicated below. Biopsy procedures will be performed following standard institutional procedures. The tissue collection goal is 3 – 6 core biopsy samples collected using an 18 - 20 gauge needle. Less than the goal amount of tissue is acceptable and should be based upon the clinical judgment of the treating investigator and the clinician performing the procedure. In the event tissue is insufficient for analysis it will not be considered a protocol violation.

- Biopsy #1 (Pre-Treatment): A mandatory fresh tumor tissue biopsy will be obtained pre-treatment from all participants.
  - The pre-treatment fresh tumor biopsy may be obtained any time before the participant's Cycle 1 Day 1 visit.
- Biopsy #2: An additional optional biopsy at the time of disease progression will be offered to all participants.
  - The time of progression biopsy should be obtained prior to the initiation of another anti-cancer therapy when possible. In the event this is not feasible, the time of progression biopsy may be obtained up to 30 days after the date that disease progression was determined. The date of progression may be considered either the date the radiological scan was performed, or the date the treating investigator judged the participant to have progressed.
  - In the event a participant enrolled to **Arm 2** crosses-over to combination treatment, the time of progression biopsy may be collected prior to cross-over and/or upon progression on combination treatment. A tumor biopsy is not required prior to the initiation of cross-over treatment.

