### 1.4 Exploratory Objectives

- Develop multivariate predictive models for response to LY3214996 alone and in combination with HCQ via integration of correlative assays, sequencing data, organoid therapeutic response measurements, and clinical data including prior regimens of therapy.
- Explore biomarker indicators of target engagement, response, and resistance.
- Investigate resistance mechanisms via repeat molecular analyses and organoid derivation at the time of progression.
- Assess the pharmacokinetic (PK) properties of LY3214996 when combined with HCQ in this patient population.

[figure not shown]

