#### 2.4.4 Evaluation of Resistance Mechanisms

Participants will be offered an optional biopsy at the time of disease progression. Time of progression biopsies will undergo repeat molecular analyses and organoid derivation to investigate mechanisms of resistance using organoid-based sensitivity profiling as well as DNA and RNA sequencing as noted above.

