### **13.5 Analysis of Exploratory Endpoints**

All participants will have a mandatory pre-treatment biopsy, and an optional time of progression biopsy will be offered to all participants. Non-parametric paired analysis will be conducted to assess the significance of changes between pre-treatment and time of progression samples.

Concordance of drug sensitivity and WTS results will be analyzed. The percentage of pre-treatment biopsies with that are above a 66% sensitivity threshold for organoid sensitivity will be determined. With a sample size of 20 per arm, we will obtain a 95% confidence interval of (36.1%, 80.9%) if we observe 60% (or 12) of the pre-treatment biopsies that are above the threshold.

Agreement between the two biopsies will be analyzed using the Kappa statistics.

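### Progression biopsies may be taken after the next anti-cancer therapy has started, and the exploratory paired and Kappa analyses do not separate them

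*Combined protocol and SAP*

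**What the plan says.** Section 9.1 (Tumor Biopsy Collection) sets the timing of the second biopsy, which is voluntary: "An additional optional biopsy at the time of disease progression will be offered to all participants". The default is clear: "The time of progression biopsy should be obtained prior to the initiation of another anti-cancer therapy when possible". The fallback follows: "In the event this is not feasible, the time of progression biopsy may be obtained up to 30 days after the date" on which progression was determined. The start of that window is itself flexible: "The date of progression may be considered either the date the radiological scan was performed, or the date the treating investigator judged" that progression had occurred. For Arm 2 participants who cross over, "the time of progression biopsy may be collected prior to cross-over and/or upon progression on combination treatment".

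The purpose of the tissue is stated in Section 1.4, "Investigate resistance mechanisms via repeat molecular analyses and organoid derivation at the time of progression", and in Section 2.4.4, "Time of progression biopsies will undergo repeat molecular analyses and organoid derivation to investigate mechanisms of resistance". Neither section excepts any subset.

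Section 13.5 gives the analysis: "Non-parametric paired analysis will be conducted to assess the significance of changes between pre-treatment and time of progression samples". It also plans Kappa statistics for agreement between the two biopsies. It does not mention therapy given between progression and biopsy, and it does not say which biopsy forms the pair for a cross-over participant.

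**The concern.** The fallback in Section 9.1 applies when a biopsy before the next therapy is not feasible. It therefore admits tissue that has already been exposed to a different drug. The protocol evidently sees the difficulty, because it prefers the earlier biopsy, but Section 13.5 does not carry that preference into the analysis.

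A new regimen can alter expression profiles and affect which cells grow as organoids. If such samples are pooled with unexposed ones, the difference from baseline mixes change on study treatment with change on the next treatment. A shift in a consistent direction raises the false-positive rate of the paired test. A change in classification lowers Kappa. Because the second biopsy is optional, pairs may be few, and each one carries weight.

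The cross-over provision raises the same question in another form. An Arm 2 biopsy taken after progression on the combination does not reflect resistance to monotherapy alone.

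At stake is the interpretation of the resistance objective. The disease control rate, its decision rule and the secondary endpoints do not use this tissue.

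**Working it through.** **The plan's own figure.** Section 13.5 gives one precision figure: 12 of 20 pre-treatment biopsies above the organoid threshold, 95% interval 36.1% to 80.9%. The exact (Clopper-Pearson) interval for 12/20 is 36.05% to 80.88%, so it reproduces. It concerns pre-treatment tissue only. No sample size, power or alpha is given for the paired or Kappa analyses, so there is no stated figure to test against this point.

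**Reading the sections together.**

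1. Section 9.1 permits a biopsy after the next therapy has started.
2. Section 2.4.4 sends progression biopsies to resistance work without exception.
3. Section 13.5 analyses progression samples without exception.
4. Sections 9.1, 10 and 13 do not ask for the start date of a later therapy. Under Section 5.6, follow-up beyond 30 days is for survival status only. The laboratory manual is not among the documents and may record the date.

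Followed as written, the plan can pool exposed and unexposed tissue, and it does not itself require the information needed to separate them afterwards.

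**Illustration of size.** All inputs are assumptions, because the documents give neither the share exposed nor the shift.

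- Paired differences are standard normal with no true change on study treatment.
- Each pair is exposed with probability f. An exposed pair is shifted by d SD, always in the same direction.
- The test is a two-sided Wilcoxon signed-rank test at 5%.
- The average shift in the data is f × d, so it runs from 0.2 × 1 = 0.2 SD to 0.3 × 2 = 0.6 SD over the main range.

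False-positive rates for d = 1 to d = 2, from 100,000 runs per setting:

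| Pairs | f = 10% | f = 20% | f = 30% |
|---|---|---|---|
| 10 | 5.7% to 6.4% | 7.8% to 11.6% | 11.2% to 20.2% |
| 15 | 6.0% to 7.6% | 9.4% to 15.9% | 15.3% to 30.1% |
| 20 | 6.4% to 8.9% | 11.1% to 20.7% | 19.4% to 39.9% |

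Shorter runs (3,000 to 6,000 per setting) agree within one to two percentage points. Across all runs, f = 20% to 30% gives about 8% to 21% with 10 pairs and about 8% to 30% with 15.

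**Sensitivity to the assumptions.**

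- Smaller shift: with d = 0.5 and f = 30%, the rate is 6.7% (10 pairs) and 7.8% (15 pairs).
- Shifts of random sign: about 5% throughout. The differences stay symmetric about zero, and the signed-rank test keeps its level under symmetry.
- Exactly 2 of 10 pairs exposed: 6.4% to 8.7%. Exactly 3 of 10: 9.6% to 15.8%.
- Five pairs: the smallest two-sided p-value is 2/2⁵ = 0.0625, so the test cannot reach 5% at all.

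**The case against.** The strongest reply is that the documents already contain the problem. The earlier biopsy is the default, the later one is a capped fallback, the sample is optional, and the analysis is exploratory with no error rate claimed. The size calculation uses an unsourced share and shift, and it needs every exposed pair to move the same way although next regimens may differ. Nearly all of this stands, and it is why the point is minor. The cap is weaker than it looks, though. It runs from progression, not from the start of the next therapy. Section 11.1 keeps scanning participants who stop treatment before progression, without saying what happens if they begin another regimen first.

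A reader might infer more than the text supports in two ways. The first is that every progression biopsy enters a resistance test and that later-therapy changes will be counted as resistance. No sentence says that all samples enter. Section 13.5 does not call its paired test a resistance test, and no rule turns a significant result into a declared mechanism. What the text supports is that nothing prevents the pooling.

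The second is that two or three exposed pairs could decide the result. With exactly two or three of 10 pairs exposed and shifted 1 to 2 SD, the test stays non-significant in at least 84% of null trials (100% − 15.8% = 84.2%).

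Exclusion also shrinks a set that may already be small. That is a fair cost, and it is the reason to keep exposed biopsies in a sensitivity analysis.

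**Conclusion.** The gap is real and minor. Section 9.1 permits a progression biopsy after another anti-cancer therapy has started. Section 13.5 does not restrict which progression samples enter the paired and Kappa analyses, so a change caused by a later therapy can be misread as resistance to the study treatment.

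The size is unknown. If 20% to 30% of pairs were exposed and shifted 1 to 2 SD in a common direction, a nominal 5% test would run at about 8% to 21% with 10 pairs and 8% to 30% with 15. At a 10% share, or with mixed directions, it stays near nominal. These figures show when the issue would matter. They do not estimate what will happen in this trial. The effect on Kappa has not been quantified. The primary conclusion is untouched.

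**What to change.** Leave biopsy timing and patient care as they are, and make three changes to data collection and analysis.

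1. Record, with each progression biopsy, the start date of any later anti-cancer therapy, or that none had begun.
2. In Section 13.5, base the main paired, Kappa and organoid resistance analyses on progression biopsies taken before that date. Report exposed biopsies separately, with one sensitivity analysis that adds them back.
3. For Arm 2 cross-over participants, use the pre-cross-over biopsy as the monotherapy pair. Report biopsies taken after progression on the combination separately.

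The cost is one date field and a few sentences in Section 13.5. The downside is that some pairs leave the main exploratory analysis: at an exposed share of 20% to 30%, 10 pairs would fall to 8 or 7, and 20 pairs to 16 or 14.
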